7.5. Known Expected Risks

Supported Biopsychosocial Self-Management

The risks associated with SSM are considered low for subjects who meet the inclusion/exclusion criteria. To further minimize risks, licensed doctors of chiropractic (DC) and physical therapists (PT) will be trained and certified by investigators, and monitored for fidelity to ensure they are implementing SSM in a manner that optimizes patient safety. Experienced investigators and consultants will be available as needed to assist DCs and PTs in managing adverse events if needed. The core elements of SSM include physical, psychological and social strategies.

Physical: Side effects associated with manual treatment and exercise are common and benign. Approximately 35% of participants in our previous BRLP trial reported expected self-limiting adverse events that were mild to moderate in severity (e.g. increased pain, soreness).²⁰

Serious adverse events following manual treatment to the lower back are rare and are estimated to occur once per million to several million visits.

Psychological and social: Subjects may experience some short-lasting emotional discomfort during and outside the sessions when practicing the psychological and social exercises and strategies (e.g. of relaxed breathing, guided imagery, pacing, relaxation, pacing, problem solving, cognitive restructuring, interpersonal communication, etc.).

Expected risks include

- Cauda equina syndrome
- Disc herniation
- Emotional discomfort
- Exacerbation of low back pain/back related leg pain, soreness or stiffness in the region treated
- Fracture
- Hematomas or hemorrhagic cysts.^{31, 146}

Medical Care

The risks associated vary depending on the medications prescribed. Choice of first and second-line medications for the study protocol was informed by the current evidence and the American College of Physicians guidelines on noninvasive treatment for LBP which balances evidence for risks and benefits when making recommendations. Licensed medical providers will care for participants randomized to medical care. Pharmacological therapies are associated with increased adverse events compared to placebo.³¹ Study providers will discuss risk/benefit profiles for specific medications with participants before making a shared decision on what medication to prescribe.

Expected risks include:

- Non-steroidal anti-inflammatory drugs (First-Line Medications)
 - Serious risks include cardiovascular events (heart attack, stroke, heart failure, high blood pressure), gastrointestinal bleeding, allergic reaction (hives, skin irritation, respiratory distress, edema), kidney failure, skin reactions, liver failure, and asthma attacks.
 - Other side effects include stomach pain, constipation, diarrhea, gas, heartburn, nausea, vomiting and dizziness.
- Second-line medications
 - Serious risks with these medications include allergic reaction, seizures, infection, hyperglycemia, bone fracture, liver or kidney damage, and addiction or abuse.
 - Other risks include sedation, drowsiness, fatigue, sleep problems, headache, weight gain, muscle weakness, mental/physical impairment, dry mouth, abdominal pain, anorexia, nausea, vomiting, gastritis, occult bleeding, dizziness, vertigo, tremor, syncope, and leukopenia.

Pilot study and supplemental aims qualitative data collection: there are few risks associated with this data collection. Risks include feeling uncomfortable answering certain questions; to minimize this, participants can decline responding to questions

7.6. Safety Monitoring

The Independent Monitoring Committee (IMC) for this study will review accruing data on a semi-annual basis to ensure:

1. The study is adequately enrolling to meet targeted goals
2. Data collection and protocol adherence rates are acceptable
3. There are no serious safety concerns

7.7. Potential Benefits

There may be no direct benefit to participants. Some participants may experience an improvement or resolution of their BRLP or associated signs and symptoms. Some participants may learn new ways to manage their BRLP on their own.

8. INTERVENTION DISCONTINUATION

Criteria for Discontinuation

Participants will be discontinued from their assigned intervention if the study interventions become contraindicated, for example:

- A serious adverse event related to treatment occurs and thus makes it unsafe to continue with the assigned intervention.
- The participant has a specific cause of BRLP and was erroneously diagnosed during screening.
- New evidence emerges and suggests it is unsafe for the participant to proceed with the intervention.

Criteria for discontinuation are met when the event is classified as serious and it is determined by the provider and/or the PI that it is unsafe to continue with the study intervention, or when a diagnosis for a specific cause of BRLP is made.

Reasons for Discontinuation

All efforts will be taken to facilitate participant's completion of the study interventions. Potential reasons for early termination include:

- Participant develops a competing comorbid health condition that precludes adherence or makes it unsafe for them to proceed with their assigned treatment.
- A change in the participant's life (e.g., participant moves, dies, has other personal matters to attend).
- Participant chooses to discontinue on their own for any reason (e.g., participant is not responding to care or getting worse).
- Study closure by institute or oversight body.

With their permission, participants will continue to be followed if the study intervention is discontinued. Participants who have discontinued treatment will be asked to complete weekly questionnaires and monthly questionnaires, if possible. Efforts will be made to accommodate participant compliance.

Temporary Discontinuation of the Intervention

Potential reasons for temporary intervention discontinuation include:

- An acute health problem arises and prohibits their ability to attend the intervention (e.g., hospitalization). The length of discontinuation will be addressed on a case-by-case basis. All attempts will be made to minimize this discontinuation.
- Participant has a scheduled vacation. Participants will be asked to limit their vacation time during the active intervention phase of the study.

Withdrawal Procedures

Participants will be asked to submit a letter or email in writing to the PI (signed and dated when possible) if they want to withdraw from the study. For reporting purposes, research staff will inquire about reasons for their withdrawal. Participants may also be asked if they're willing to complete self-report questionnaires as a means of collecting primary and secondary outcomes. If they refuse, participants will not be contacted by the study team. A formal letter will be sent by the PI, or designee, indicating receipt of their request for withdrawal and additional provisions around data collection, if applicable. The letter will reiterate our appreciation for their participation to date and remind participants that their withdrawal will not affect their relationship with the university. Further, regulatory bodies will be provided summary information related to attrition (e.g., losses to follow-up, withdrawals etc.). Individual participants will not be named.

Termination Procedures

This research may be discontinued at any time by the UMN IRB, the NIH, OHRP, UMN, or other government agencies as part of their duties to ensure research participants are protected.

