7.2 Adverse Event Identification

Adverse events will be identified in the following ways:

- Following enrollment, participants will be asked about the occurrence of AE/SAEs by their treatment provider at every visit.
- Participants will be informed to report AE/SAEs directly to study staff throughout the study period
- Participants will be asked if they experienced any AE/SAEs during their monthly self-report questionnaires.

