7.3 Follow-up for Adverse Events

Events will be followed until resolution or stabilization, whichever occurs first; resolution and stabilization will be determined by the PI with input from the study clinician when appropriate.

AEs During the Intervention Phase

If an AE/SAE occurs during the intervention phase, the study clinician or designee will obtain information about the event, which will be used by the PI to assess the severity, expectedness and relatedness to the study. The study clinician will monitor the AE/SAE while the participant is under their care; this will include a medical evaluation and treatment, or modifications to treatment as necessary to protect the participant and minimize harm. If warranted, referral to an outside provider will be made. Participants who cannot continue with the study intervention due to safety concerns will be removed from the intervention and/or study when warranted. See Study Discontinuation.

The rescue medication protocol may apply. See Rescue Medication.

AEs During the Monthly Follow-Up (M1-M6)

If an AE/SAE occurs during the follow-up phase, study staff (clinician, coordinator, PI or designee) will contact the participant (or their emergency contact with the participant's permission), to obtain information about the event, including but not limited to what happened, when the event occurred, and treatment rendered. This information will be used by the PI to assess the severity, expectedness and relatedness to the study.

Events will be followed for outcome information until resolution or stabilization. Resolution and stabilization will be determined by a PI with input from the study clinician when appropriate.

The PI or designee will record all reportable events with start dates occurring any time after enrollment until 7 (for non-serious AEs) or 30 days (for SAEs) after the last day of study participation.

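### At withdrawal, declining outcome questionnaires ends study contact with no safety exception, and this is not reconciled with the adverse event follow-up and 7/30-day recording rules in Section 7.3

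*Combined protocol and SAP*

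**What the plan says.** Section 8, Withdrawal Procedures, covers people who leave the study, as distinct from people who only stop treatment. Staff ask why: "research staff will inquire about reasons for their withdrawal". Participants may then be asked whether they will "complete self-report questionnaires as a means of collecting primary and secondary outcomes". The consequence of saying no is: "If they refuse, participants will not be contacted by the study team". One outgoing letter follows: "A formal letter will be sent by the PI, or designee, indicating receipt of their request for withdrawal". The letter also covers any further arrangements for data collection.

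Section 7.3 sets the safety duties. On open events: "Events will be followed until resolution or stabilization, whichever occurs first". On method: "If an AE/SAE occurs during the follow-up phase, study staff (clinician, coordinator, PI or designee) will contact the participant", or an emergency contact if the participant permits. On the recording cut-off, reportable events starting after enrollment are recorded "until 7 (for non-serious AEs) or 30 days (for SAEs) after the last day of study participation".

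Section 7.2 lists three ways in which events come to light: provider questions at each visit, reports that participants make to staff, and the monthly survey ("Participants will be asked if they experienced any AE/SAEs during their monthly self-report questionnaires"). Table 5 schedules adverse event collection at intervention visits and in the monthly surveys for months 1 to 6, and its footnote allows participants to report at any point in the trial. Section 7.1 adds that serious events are collected passively through ad hoc reports as well as at study visits.

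**The concern.** The only question put to a withdrawing participant is about outcome questionnaires. A person may be tired of surveys yet willing to take one call about an unresolved event. Section 8 gives them no way to say so and treats the first refusal as covering the second. Section 7.3, read alone, tells staff to keep following that event, and to do so by contacting the participant.

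What is at stake is the completeness of the safety record and the team's ability to learn how an event ended. Section 7.1 plans to compare adverse event rates between the arms, and Section 7.6 and Table 8 send those data to the independent monitors. With 40 to 50 participants, a few incomplete records would be noticeable in such a summary. Section 7.4 also dates awareness of an event from when the team can discuss it with the participant or a designee, so contact bears on reporting as well as on counting.

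**Working it through.** No calculated figure is involved. The check is a comparison of the sections.

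1. **Who falls under the no-contact rule.** Section 8 says that people who stop the intervention continue to be followed, with permission, and are asked for weekly and monthly questionnaires. The rule therefore reaches only those who withdraw from the study and also decline questionnaires.

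2. **What the refusal covers.** The request is framed around primary and secondary outcomes. Section 9.4 defines these as feasibility and protocol refinement measures, and adverse events are not among them. Safety contact is not offered as a separate choice.

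3. **Exceptions.** Section 8 has no exception for open events. Section 7.3 has no exception for withdrawn participants. Neither refers to the other on this point.

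4. **What remains for this group.** Taking the Section 7.2 routes in turn:
   - Visits: end when the person leaves.
   - Monthly survey: ends with the refusal.
   - Participant-initiated report: remains open.
   - Ad hoc reports of serious events (Section 7.1): remain open.
   - The question about the reason for withdrawal (Section 8): asked once, with no adverse event question specified.

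   Active ascertainment stops and passive reporting remains.

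5. **The 7/30-day window after withdrawal.** The last day of study participation is not defined for withdrawals. If it is the withdrawal date, the window opens just as contact closes. If it is some other date, the plan does not say which.

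6. **The window for completers.** The last scheduled adverse event question is in the month 6 survey. Close-out in Section 6.2.4 is a notice that participation has ended. Neither Table 5 nor Section 7.2 schedules a question after that, so capture inside the window is passive for completers as well.

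7. **Size.** The documents give no rate of withdrawal combined with refusal, and no rate of events open at withdrawal or starting in the window. The number of people affected cannot be derived.

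**The case against.** The best case against the point has four parts.

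- **The sections can be read together.** Someone who leaves a study and declines further data collection has limited what the team may do, and Section 7.3 can be read as operating within that permission. It speaks of monitoring while the participant is under the clinician's care, and makes use of an emergency contact conditional on permission. On this reading a clarifying sentence is missing. That is a fair description of the remedy, but it does not remove the problem: as written, Section 8 cuts off safety follow-up from people who declined only surveys.
- **The 7/30-day rule is a recording cut-off.** Section 7.3 does not promise active questioning in the window, and Section 7.1 declares passive reporting as one method of collecting serious events. This stands. The gap for completers is that the plan does not say the window relies on passive reporting.
- **The consequence is small.** This is a feasibility pilot. No target in Table 6 and no analysis in Section 9.5 depends on adverse event rates. This stands too.
- **Some loss is unavoidable.** A participant may refuse every kind of contact, and that must be respected.

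A reader might infer more than the text supports. That such participants are never contacted is too strong, since the reason is asked and a letter is sent, and an event that prompted withdrawal may surface then. That safety data are lost is also too strong: nothing says that data already collected are discarded, and passive routes stay open. That these are the people most likely to have events has no figure behind it. Section 8 mentions getting worse as an example of why someone might stop the intervention, and those people stay in follow-up with permission. Section 7.3 does foresee removal from the intervention or the study for safety reasons, so a link is plausible, but it is not quantified.

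**Conclusion.** Section 8 and Section 7.3 are unreconciled for participants who withdraw and decline questionnaires. In that group, open events and events starting in the 7/30-day window may be incompletely captured, because only participant-initiated or ad hoc reports remain once the reason has been asked and the letter sent. For completers, capture inside the window is also passive, and the plan does not say so.

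The group is narrow and its size is unknown. It might seem natural to size it from the month 6 completion target in Table 6, but missing a survey includes ordinary non-response, which Section 10.3.4 lists separately from formal withdrawal. Multiplying the sample by 30 days would likewise say nothing about missed events without an event rate. Neither gives a usable magnitude.

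The conclusion rests on reading the no-contact sentence as it stands and on no other study document supplying a safety exception. Sample size, feasibility targets and planned analyses are unaffected. The change is worth making because it is cheap and improves both participant safety and the completeness of the adverse event record.

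**What to change.** - In Section 8 and on the withdrawal form, ask two separate questions: (a) whether the participant will complete questionnaires, and (b) whether they may be contacted about safety only. Apply the no-contact rule only if (b) is also declined.
- Ask the standard AE/SAE question at the same time as the reason for withdrawal.
- Define the last day of study participation for withdrawals, so that the 7/30-day window has a start date.
- Add a cross-reference between Section 7.3 and Section 8 so that each states how the other applies.
- Optionally, send one automated REDCap AE/SAE query 30 days after the last day of participation to everyone who has not declined (b). Otherwise, state that the window relies on passive reporting. This step is not needed to reconcile the two sections.

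The cost is protocol and form wording, plus at most one brief extra contact per participant and a slightly later final close-out if the query is adopted.

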9. STATISTICAL CONSIDERATIONS

9.1. General Design Issues

We will conduct a parallel, two-group randomized pilot study in preparation for a future phase II multi-site randomized clinical trial. A total of 40-50 participants with chronic back-related leg pain (BRLP) will be randomly assigned to either 12 weeks of: 1) Supported Self-Management (SSM) or 2) Medical Care. The pilot study will assess the feasibility of key methods and procedures to be used in the larger randomized trial. The aims of the pilot study are to:

1. To conduct a Planning Phase to develop detailed protocols and procedures, train project personnel, and secure necessary oversight approvals.
2. To assess future trial feasibility through achievement of pre-specified targets for:

- a. Recruiting and enrolling individuals with chronic BRLP by assessing recruitment rates; enrollment rates; and screened participants' views and perspectives
- b. Delivering experimental and comparison interventions by assessing acceptability and adherence; provider intervention fidelity rates; and participant and provider views
- c. Data collection by assessing follow up rates of future clinical trial outcome measures

9.2. Sample Size

The sample size for this pilot study has been informed by previous pilot studies by the investigators, who have found approximately 15-20 participants per group sufficient for informing the feasibility of larger, randomized clinical trials. The feasibility of recruitment, enrollment, intervention acceptability and credibility, participant adherence, provider fidelity, and data collection activities will be assessed using designated feasibility measures and targets. Protocol refinement measures will be collected using qualitative and quantitative methods to identify areas for modification in the future trial. Because of the relatively small number of providers needed for a pilot study, and budget restrictions, we will also engage our consultants and The Clinician Advisory Panel to provide input to the development and subsequent revisions of the intervention and training protocols.

9.3. Treatment Assignment Procedures

Enrolled subjects will be randomized using blocked randomization (with varying block sizes) following stratification for back-related leg pain classification (QTF classification 2, 3, or 4).⁹⁵ Computer generated random treatment assignments will be generated by an independent study statistician and conveyed electronically through REDCap (the electronic study database) at the time of enrollment to preserve allocation concealment. Screening clinicians and study staff will be blinded to upcoming treatment assignments.

9.4. Outcomes

9.4.1. Primary Outcomes

Primary outcomes for the pilot study are feasibility measures for the larger randomized trial including:

- Recruitment feasibility - Number of participants screened per month; percentage of screened participants who are female; percentage of screened participants who are minorities; participant views and perspectives on research participation
- Enrollment feasibility - Number of participants enrolled per month; percentage of enrolled participants who are female; percentage of enrolled participants who are minorities; participant views and perspectives on research participation
- Intervention acceptability and credibility feasibility - Percentage of enrollees not receiving any treatment; percentage of enrollees receiving prohibited treatments during the 12-week intervention phase (contamination); percentage of enrollees satisfied with treatment

- Participant treatment adherence feasibility - Percentage of enrollees attending required sessions; percentage of enrollees in the supported biopsychosocial self-management group reporting participation in home practice; percentage of enrollees in medical care group reporting taking medications as prescribed
- Provider fidelity feasibility - Percentage of provider visits where 100% of required intervention activities were delivered
- Data collection feasibility - Percentage of enrollees completing the month 3 assessment; percentage of enrollees completing the month 6 assessment; percentage of weekly pain severity and frequency assessments completed

Table 6. Feasibility Measures & Targets

Recruitment	≥40 screened/month (50% women, 25% minorities)
Enrollment	≥8 enrolled/month (50% women, 25% minorities)
Intervention acceptability, credibility	≤10% never receive any treatment; ≤10% receive prohibited treatments during 12-week intervention phase (contamination) ≥80% satisfied with treatment
Participant adherence	≥80% participants attend required sessions (SSM=4; MC=2) ≥70% of SSM participants report participation in home practices ≥70% of MC participants report taking medications as prescribed
Provider fidelity	Providers deliver 100% of required intervention activities on ≥70% of visits
Data collection	≥85% of participants complete 12 weeks follow up ≥80% of participants complete 25-week follow up ≥80% of weekly pain severity and frequency surveys completed

